5.2 Eliciting and Reporting Adverse Events

The investigator or subinvestigator will periodically assess subjects for the occurrence of AEs. To avoid bias in eliciting AEs, subjects should be asked the non-leading question: "How have you felt since your last visit?" All AEs (serious and nonserious) reported by the subject must be recorded in the source documents and CRFs provided by the sponsor. The event name, date and time of onset, date and time of recovery, seriousness, severity, causal relationship to IMP, actions taken regarding IMP administration, and outcome thereof will be recorded in the CRF. The period for AE and SAE collection is defined as the period after evaluation at Week 10 of Trial 331-102-00088 until the end-of-trial date.

Use medical terminology in AE reporting. Adverse events should be reported as a single unifying diagnosis whenever possible or, in the absence of a unifying diagnosis, as individual signs or symptoms. Exacerbation or disease progression should be reported as an AE only if there are unusual or severe clinical features that were not present, or experienced earlier, or not expected on the basis of the course of the condition.

Worsening of severity and seriousness of reported AEs must be reported as new AEs in the CRF.

In addition, the sponsor must be notified immediately by e-mail of any IREs according to the procedure outlined below, in [Section 5.3 Immediately Reportable Events](#). Special attention should be paid to recording hospitalization and concomitant medications.

5.3 Immediately Reportable Events

The investigator, subinvestigator, or designee must report any and all IREs (see [Section 5.1 Definitions](#)) to the sponsor by e-mail (using the contact information on the title page of this protocol) immediately after either the investigator, subinvestigator, or designee becomes aware of the event. An IRE form must be sent by e-mail to the sponsor. Please note that the IRE form is NOT the AE section of the CRF. Due consideration must be given to the subject's privacy when an IRE form is sent by e-mail.

For subjects experiencing SAEs or IREs, such events should be followed until the events are resolved or clinically stabilized, or the subject is lost to follow-up. *Resolved* means that the subject has returned to the baseline state of health, and *stabilized* means that the investigator or subinvestigator does not expect any further improvement or worsening of the subject's condition. It is expected that the investigator or subinvestigator will provide or arrange appropriate supportive care for the subject and will provide prompt updates on the subject's status to the sponsor.

5.4 Potential Drug-induced Liver Injury

For a subject who experiences an elevation in aspartate aminotransferase (AST) or alanine aminotransferase (ALT) that is ≥ 3 times the ULN, total bilirubin level should also be evaluated. If the total bilirubin is ≥ 2 times the ULN, complete the IRE form and so on with all values listed and also report as an AE in the CRF.

5.5 Pregnancy

Women of childbearing potential are defined as female subjects for whom menstruation has started and who are not documented as sterile (ie, have had a bilateral oophorectomy and/or hysterectomy or who have been postmenopausal for at least 12 months).

For WOCBP and for men who are sexually active, there must be a documented agreement that the subject and/or their partner will take effective measures (ie, double barrier method) to prevent pregnancy during the course of the trial and for 30 days after the final administration of IMP. Unless the subject or their partner is sterile (ie, women who have had a bilateral oophorectomy and/or hysterectomy or who have been postmenopausal for at least 12 consecutive months; or men who have had a bilateral

orchidectomy) or remains abstinent, 2 of the following precautions must be used: vasectomy, tubal ligation, vaginal diaphragm, IUD, oral contraceptives, or condom with spermicide. Any single method of birth control, including vasectomy and tubal ligation, may fail, leading to pregnancy. The contraceptive method will be documented at each trial visit.

Before enrolling WOCBP in this clinical trial, investigators or subinvestigators must review the below guidelines about trial participation with all WOCBP. The topics should generally include:

- General information
- Informed consent form
- Pregnancy prevention information
- Drug interactions with hormonal contraceptives
- Contraceptives in current use
- Guidelines for the follow-up of a reported pregnancy

Before trial enrollment, WOCBP must be advised of the importance of avoiding pregnancy during trial participation and the potential risk factors for an unintentional pregnancy. The subject must sign an informed consent form stating that the above-mentioned risk factors and the consequences were discussed with her.

All WOCBP must undergo a urine or serum pregnancy test (human chorionic gonadotropin [HCG] test) at evaluation at Week 10 of Trial 331-102-00088. If a urine test is performed and is positive, the investigator or subinvestigator will follow up with a confirmatory serum test.

During the trial, all WOCBP should be instructed to contact the investigator or subinvestigator immediately if they suspect they might be pregnant (eg, missed or late menstrual cycle).

If a subject is suspected to be pregnant before initiation of IMP treatment, the IMP administration must be withheld until the results of pregnancy tests are available. If the pregnancy is confirmed, the subject must not receive the IMP and must not be enrolled in the trial. If pregnancy is suspected while the subject is taking IMP, the IMP must be withheld immediately (if reasonable, taking into consideration any potential withdrawal risks) until the result of the serum pregnancy test is known. If pregnancy is confirmed, the IMP will be permanently discontinued in an appropriate manner (eg, dose tapering if necessary for subject safety) and the subject will be withdrawn from the trial. (Exceptions to trial discontinuation may be considered for life-threatening conditions only after

consultations with the PV department [see the cover page of this protocol for contact information].)

The investigator or subinvestigator must immediately notify the sponsor of any pregnancy associated with IMP exposure during the trial and for 30 days after the final administration of IMP, and record the event on the IRE form, and forward it to the sponsor. The sponsor will forward Pregnancy Surveillance Form(s) for monitoring the outcome of the pregnancy. The same applies to the pregnancy of a subject's partner.

Protocol-required procedures for trial discontinuation and follow-up must be performed on the subject unless contraindicated by pregnancy (eg, x-ray studies). Other appropriate pregnancy follow-up procedures should be considered, if indicated. In addition, the investigator or subinvestigator must report to the sponsor, on appropriate Pregnancy Surveillance Form(s), follow-up information regarding the course of the pregnancy, including perinatal and neonatal outcome. Infants will be followed for a minimum of 6 months from the date of birth.

5.6 Procedure for Breaking the Blind

Not applicable.

5.7 Follow-up of Adverse Events

5.7.1 Follow-up of Nonserious Adverse Events

Nonserious AEs that are identified at any time during the trial must be recorded in the AE section of the CRF, with the current status (ongoing or resolved/recovered) noted. All nonserious events (other than IREs) that are ongoing at the end-of-trial date (final day of observation) will be recorded as ongoing in the CRF. For any AE having been identified throughout the trial, during data analysis, additional relevant medical history information may be requested by the sponsor to further ascertain causality (including, but not limited to, information such as risk-related behavior, family history, and occupation). The follow-up information after the end-of-trial date (final day of observation) will be recorded in the subject's medical record.

5.7.2 Follow-up of Serious Adverse Events and Immediately Reportable Events

This trial requires that subjects be actively monitored for SAEs and IREs up to the end-of-trial date (final day of observation).

Serious AEs and IREs that are identified or ongoing at the end-of-trial date must be recorded in the AE section of the CRF. Between the end-of-trial date for the individual

subject and the end-of-trial date for the last subject, if any new information regarding an SAE or IRE becomes available (eg, the event is resolved), this must be reported to the sponsor using the IRE form and so on, and the information must be recorded in the AE section of the CRF. The investigator or subinvestigator will follow SAEs and IREs, and will continue to report any significant information to the sponsor until the events are resolved or stabilized, or the subject is lost to follow-up or has died, using the IRE form and so on.

5.7.3 Follow-up and Reporting of Serious Adverse Events and Immediately Reportable Events Occurring After the End-of-trial Date (Final Day of Observation)

Any new SAEs or IREs reported to the investigator or subinvestigator, which occur after the end-of-trial date (final day of observation) and are determined by the investigator or subinvestigator to be associated with the use of the IMP, should be reported to the sponsor. This includes SAEs and IREs that are captured on follow-up telephone contact or at any other time point after the defined trial period. The investigator or subinvestigator will follow SAEs and IREs identified after the defined trial period and continue to report any significant follow-up information to the sponsor until the events are resolved or stabilized, or the subject is lost to follow-up or has died, using the IRE form and so on.

6 Statistical Analysis

The definitions of the datasets for analysis and the analysis methods for the specified endpoints are described below. The statistical analysis plan details are described in a separate Statistical Analysis Plan. The Statistical Analysis Plan will be finalized prior to data lock.

6.1 Determination of Sample Size

This trial aims to include 100 completers of brexpiprazole treatment in Trial 331-102-00088 as subjects who will continue to receive brexpiprazole for more than 10 weeks. Since patients are assigned to the 1 mg group, the 2 mg group, or the placebo group at a ratio of 3:4:4 in Trial 331-102-00088, the target sample size for this trial (331-102-00184) has been determined to be 157 subjects, taking into account some of them have received placebo in the previous trial.

6.2 Datasets for Analysis

Analyses in this trial will be performed for each of the following groups unless otherwise specified:

- Rollover subjects from the brexpiprazole group in Trial 331-102-00088
- Rollover subjects from the placebo group in Trial 331-102-00088
- All subjects (rollover subjects from the brexpiprazole group + rollover subjects from the placebo group)

6.2.1 Efficacy Analysis Set

The efficacy analysis set will comprise subjects who have received at least 1 dose of the IMP and from whom CMAI total scores have been obtained at baseline and at least 1 time point after initiation of treatment.

6.2.2 Safety Analysis Set

The safety analysis set will comprise subjects who have received at least 1 dose of the IMP.

[figure not shown]
6.3 Handling of Missing Data

For analyses at the final assessment, the last observation carried forward (LOCF) method (in which missing Week 14 data are imputed by the data which were observed after initiation of IMP treatment and obtained immediately before Week 14) will also be used.

6.4 Efficacy Endpoint Analyses

Efficacy analyses will be performed on the efficacy analysis set. Baseline is defined as the last data obtained prior to initiation of IMP treatment in this trial.

- CMAI total score
- CGI-S
- CGI-I

A series of six horizontal black bars of varying lengths, representing redacted text. The first bar is the longest, followed by a shorter one, then a longer one, then a shorter one, then a longer one, and finally a very long one at the bottom.

For endpoints other than CGI-I, descriptive statistics of actual measurements and changes from baseline at each time point and the final assessment (Week 14 LOCF) will be calculated. For CGI-I, descriptive statistics of actual measurements at each time point and the final assessment (Week 14 LOCF) will be calculated.

6.4.1 Interim Analysis

In this trial, safety will also be evaluated by the IDMC, when approximately 25%, 50%, and 75% of the target number of subjects in the preceding Trial [contact] have completed or discontinued the trial. Additional evaluation by the IDMC may be performed depending on the status of subject enrollment into the current trial (331-102-00184).

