3.1 Type/Design of Trial

This is a multicenter, uncontrolled, open-label trial to evaluate the efficacy and safety of brexpiprazole in patients with agitation associated with dementia of the Alzheimer's type who require medication. The overview of the trial design is shown in Figure 3.1-1.

The trial consists of a screening period, a treatment period, and a follow-up period. The investigator or subinvestigator will explain the details of the trial to prospective subjects (if the investigator or subinvestigator judges that the subject is incapable of providing informed consent, or if the subject is hospitalized for reasons related to medical protection, the subject's legally acceptable representative must provide written consent, and even when written consent is obtained from the legally acceptable representative, the subject should be given an explanation appropriate to his or her level of understanding and, if possible, should also provide written consent) and their main caregivers using the explanatory materials and informed consent form (ICF) and obtain written consent for participation in the trial from the prospective subjects (or their legally acceptable representatives) and caregivers during Trial 331-102-00088 between the dates of evaluation at Week 4 and Week 10. The investigator or subinvestigator will assess the eligibility of subjects to participate in the trial based on observations, tests, and investigations performed during the treatment period of Trial 331-102-00088. All subjects judged to be eligible based on the results of observations, tests, and investigations in Trial 331-102-00088 will skip the follow-up observation of Trial 331-102-00088 and be rolled over into the treatment period of this trial (331-102-00084). Subjects will receive brexpiprazole for 14 weeks, starting at 0.5 mg, followed by dose titration, and then at either 1 or 2 mg, according to [Section 3.2 Trial Treatments](#), and will undergo periodic observation, tests, and investigations to assess efficacy and safety. IMP administration will begin no later than 10 days after the date of evaluation at Week 10 of Trial 331-102-00088. The subject will return to the trial site 28 days after the completion

of IMP administration for follow-up observation. Discontinued subjects will also undergo follow-up observation.

For subjects who discontinued the trial during the treatment period, the examination at discontinuation will be performed.

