3.8.7 Independent Data Monitoring Committee (IDMC)

In order to avoid exposing subjects to any potential risks (including the risk of death) during the trial period and to ensure the safe conduct of the trial, the IDMC established in Trial 331-102-00088 will monitor the current trial (331-102-00184) as well. The IDMC will meet either regularly as specified in the protocol of Trial 331-102-00088 and as needed to review the subject demographics and AEs and to give advice on the appropriateness of continuing the trial or the necessity of modifying the protocol.

The sponsor will designate the following as IDMC members: [REDACTED]

The IDMC members, their roles, and other details will be specified in a separate procedure.

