9.7.3 S-STS

For the score for each S-STS item (2 through 14), total score, suicidal ideation subscale score, and suicidal behavior subscale score, descriptive statistics of actual measurements

and changes from baseline at each time point and the final assessment (Week 14 LOCF) will be calculated.

10 Pharmacokinetic Analyses

Not applicable.

11 Pharmacodynamic Analyses

Not applicable.

12 Pharmacogenomic Analyses

Not applicable.

13 Analysis of Other Endpoints

Analysis of other endpoints will be performed using the safety analysis set. Baseline is defined as the last data obtained prior to initiation of IMP treatment.

- ADCS-ADL
- MMSE

For ADCS-ADL total score and MMSE total score, descriptive statistics of actual measurements and changes from baseline at each time point and the final assessment (Week 14 LOCF) will be calculated.

14 Interim Analysis

In this trial, safety will also be evaluated by the IDMC, when approximately 25%, 50%, and 75% of the target number of subjects in the preceding Trial 331-102-00088 have completed or discontinued the trial. Additional evaluation by the IDMC may be performed depending on the status of subject enrollment into the current trial (331-102-00184).

A statistical analysis plan for interim analysis is described in a separate interim analysis plan.

15 Changes in the Planned Analyses

[REDACTED]

The following changes were made to categorical analyses of QTc:

- Only subjects with postdose QTc meeting the criteria will be summarized, instead of summarization at all time points.
- Only subjects with QTc not meeting the criteria at baseline and meeting the criteria after baseline will be summarized.

16 References

Not applicable.

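### Are subjects in this trial left without required IDMC review once the preceding trial passes its 75% point?

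*Protocol*

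**What the plan says.** Protocol Section 6.4.1 provides that the IDMC will also evaluate safety in this trial "when approximately 25%, 50%, and 75% of the target number of subjects in the preceding Trial" have completed or discontinued. SAP Section 14 repeats the rule and names the trial in which the count is taken: "25%, 50%, and 75% of the target number of subjects in the preceding Trial 331-102-00088 have completed or discontinued the trial". Both sections then add a conditional review: "Additional evaluation by the IDMC may be performed depending on the status of subject enrollment into the current trial". SAP Section 14 closes by pointing elsewhere for the statistical detail: "A statistical analysis plan for interim analysis is described in a separate interim analysis plan".

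These sections are not the only text on the committee. Protocol Section 2.1 states that the committee set up for the preceding trial monitors safety in this one too. Protocol Section 3.8.7 repeats this, gives the committee the task of advising on continuation or protocol changes, and sets its meeting pattern: "The IDMC will meet either regularly as specified in the protocol of Trial 331-102-00088 and as needed". It leaves the rest to another document: "The IDMC members, their roles, and other details will be specified in a separate procedure".

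**The concern.** All three stated milestones run on another trial's clock, and the only review linked to this trial's enrolment is optional. Extension treatment trails the preceding trial: "IMP administration will begin no later than 10 days after the date of evaluation at Week 10 of Trial 331-102-00088", and dosing then lasts 14 weeks. A subject who completes the preceding trial just before a milestone has almost no extension data at that review. Anyone on treatment at the 75% point, or rolling over later, is exposed further with no later review fixed in these two sections.

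This would matter because safety is the trial's first objective. The committee exists "to avoid exposing subjects to any potential risks (including the risk of death) during the trial period", and Protocol Section 1.1 cites a 1.54-fold higher mortality with atypical antipsychotics in dementia. If monitoring really ended at the preceding trial's 75% point, a late safety signal might not reach the committee in time.

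**Working it through.** **1. What the text requires.** Four provisions have to be read together.

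- Protocol 6.4.1 and SAP 14: three required evaluations of this trial's safety, timed by the preceding trial.
- The same two sections: further evaluation, dependent on enrolment into this trial.
- Protocol 3.8.7: regular meetings under the preceding trial's protocol, plus meetings as needed.
- Protocol 3.8.7 and SAP 14: remaining detail in a separate procedure and a separate interim analysis plan.

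The first provision alone suggests that monitoring stops at 75%. The other three show that it does not. What is missing is only a fixed later date in these two documents, and three documents not available here may supply one.

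**2. Whether any result depends on the dates.** SAP Section 6 plans no primary or secondary outcome variables, and the planned analyses are descriptive. No test is repeated and no error rate is spent at a look. The target size does not depend on the reviews either: 100 / (7/11) = 157.1, which reproduces the stated 157.

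**3. How much exposure could follow the 75% point.** The documents do not give the preceding trial's size, accrual or rollover, so this is illustration only.

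Inputs:
- 157 subjects and 14 weeks of dosing, from the documents.
- The planned calendar, November 2018 to February 2022, is 165.6 to 173.6 weeks. Subtracting 20 weeks (stated maximum participation) from the shorter span and 18 weeks (14 of dosing plus 4 of follow-up) from the longer leaves about 146 to 156 weeks for entry.
- Assumed: the preceding trial's subjects finish evenly over 150 weeks, so its 75% point is at week 112.5. Entry is uniform, with no dropout, and the review falls on the milestone day.

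Let E be the weeks of entry and t the weeks from first entry to the review. For t between 14 and E, the share of exposure after the review is 1 − (t − 7)/E. If entry has been closed for 14 weeks or more, the share is zero.

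| Entry pattern | E | t | Share after the 75% review | Subjects with exposure after it |
|---|---|---|---|---|
| Steady, weeks 0 to 150 | 150 | 112.5 | 1 − 105.5/150 = 29.7% | 39.2 + 14.7 = 53.9 (34%) |
| Opens at week 45 | 105 | 67.5 | 1 − 60.5/105 = 42.4% | 56.1 + 20.9 = 77.0 (49%) |
| Closes at week 112.5 | 112.5 | 112.5 | 7/112.5 = 6.2% | 157 × 14/112.5 = 19.5 (12%) |
| Closes by week 98.5 | ≤ 98.5 | 112.5 | 0% | 0 |

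The last row is possible because the target is fixed at 157 while the preceding trial's size is not stated, so entry could fill early. A 10-day start lag (1.43 weeks) adds about 1 percentage point to each of the first three rows. It moves the last cut-off from week 98.5 to 112.5 − 14 − 1.43 = week 97.1.

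Under steady accrual the three required reviews are far from empty. At weeks 37.5, 75 and 112.5 they would cover 30.5/150 = 20%, 68/150 = 45% and 105.5/150 = 70% of all extension exposure. At the third, (112.5 − 14)/150 = 66% of subjects, about 103, would have finished 14 weeks.

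**4. Whether a fixed review would clearly do better.** Consider a required review when 75% of this trial's own subjects have finished, with a fallback about 7 weeks after the preceding trial's 75% review if the first trigger would come too early or never.

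- Steady entry: the review falls at 112.5 + 14 = week 126.5, and the share left after it is 1 − 119.5/150 = 20.3%, against 29.7%.
- Entry over 132 weeks: it falls at 0.75 × 132 + 14 = week 113, half a week after the week-112.5 review. The share left goes only from 1 − 105.5/132 = 20.1% to 1 − 106/132 = 19.7%, so the meeting nearly duplicates the one before it.
- Entry closed by week 98.5: the fallback at week 119.5 would convene the committee with nobody on treatment.

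The fixed rule helps under some accrual patterns and is idle under others. A review conditional on enrolment adapts to each of them.

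**The case for a change.** The strongest reply is that none of the other provisions fixes a date. The regular meetings again follow the other trial's protocol, as-needed meetings depend on someone seeing a need, and the enrolment-linked review is discretionary. In a drug class with a recognised mortality risk, a safety extension should perhaps commit to one review on its own clock, at the cost of one data package and one meeting.

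The factual part stands: read alone, Protocol 6.4.1 and SAP 14 name no required review after the preceding trial's 75% point. It does not follow that oversight lapses. The committee's remit covers this trial without an end at 75%. The trial is open-label, so events are not masked from the sponsor. Every SAE is immediately reportable (Protocol Sections 5.1 and 5.3), and Protocol Section 3.9.1 contemplates suspension or termination by the sponsor for any reason. It also cannot be said that the later review is missing, because the documents that would contain it were not available.

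**Conclusion.** The concern does not hold. The wording is as described, but the plan contradicts nothing and, followed as written, makes no result or conclusion wrong. Oversight of this trial continues under Protocol Sections 2.1 and 3.8.7, and the conditional review already turns on the quantity that matters, this trial's enrolment.

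The effect on estimates, error rates and sample size is nil. The share of exposure after the preceding trial's 75% point is not determined by the documents. It is 0% to about 42% across the patterns tried, all of which rest on assumed uniform entry and an assumed 150-week accrual. What remains is a preference about scheduling, or at most a convenience for the reader: a cross-reference to wherever the IDMC calendar is kept.
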